The primary analysis will compare change in accuracy of naming untrained items between groups (A-tDCS versus sham) in a two-sample *t*-test for the Intent-to-treat sample. For participants who do not complete the Week 1 post-treatment assessment, the post-treatment value will be imputed using a multiple imputation approach assuming a monotone missing mechanism and missing is at random (MAR). As a sensitivity analysis, the primary outcome analysis will be repeated using all available follow-up data (without explicit imputation) in a mixed effects model of the change from baseline in naming accuracy adjusted for baseline (with Week 1, 5, or 20 as a categorical variable and a random effect for subject). Similar analyses will be done for the change in accuracy of trained items.

If we accept the null hypothesis, then tDCS is considered clearly ineffective (in improving anomia in stroke patients) and will not be considered for further study. If we reject the null hypothesis, we would consider undertaking a Phase III study of tDCS.

Sample Size Determination

We expect to enroll 50 participants over 4 years, and expect 40-45 will complete the study. We predict no difficulty recruiting at least 10-15 participants with aphasia each year after subacute stroke, as the PI has

Date: March 2, 2021

Principal Investigator: [name], MA

Application Number: IRB00089018

recruited an average of 53 aphasic patients due to acute left hemisphere ischemic stroke each year in her previous studies of aphasia recovery. If sample size in each group is 20, (a total sample size of 40), we will have 89% power to detect a difference in means of 23 (the difference between a A-tDCS mean change in accuracy, μ_1 , of 33 and a sham mean change in accuracy, μ_2 , of 10) assuming that the standard deviation of change for both groups is 22.2 using a two group *t*-test with a two-sided alpha of 0.05. These mean changes for tDCS and sham and standard deviation of change are based on the one published sham-controlled study of tDCS combined with SALT in subacute stroke.

Multiplicity

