2. STATISTICAL ANALYSIS PLAN AND STATISTICAL REPORTS

This document provides the details of the statistical analyses planned for the trial. Prior to locking the database and breaking the code, this Statistical Analysis Plan (SAP) will be updated. The final SAP will define all “pre-specified, pre-planned analyses” and will trump the protocol.

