8. PRIMARY ANALYSIS

8.1 Primary Outcome

The primary outcome will be the change in the number of correctly named items on the PNT (absolute change from pre-treatment and immediate post-testing). The PNT is administered twice (and averaged to reduce variability) on two consecutive days immediately before treatment starts and twice after treatment is completed. The change will be computed as the difference in the number of correctly named items between the average of the two pre-treatment assessments to the average of the two post-treatment sessions.

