8.5 Missing Data

For the primary analysis, for participants who do not complete the 1 week post-treatment assessments, the post-treatment value will be imputed using a multiple imputation approach assuming a FCS missing mechanism and missing is at random (MAR).

As a sensitivity analysis with the modified ITT sample, the primary outcome analysis will be repeated using all available follow-up data (without explicit imputation) in a mixed effects model of the change from baseline in naming accuracy adjusted for baseline (with week (1, 5, or 20 weeks post-treatment) as class variable and a REPEATED statement). The model will include the baseline covariates used for the primary analysis as fixed effects.

The statistical model will be a repeated measures model (SAS® MIXED procedure with REPEATED subcommand) assuming a compound symmetry (CS) covariance structure.

```
PROC MIXED;
  CLASS SUBJID ARM VISITNUM TYPE;
  MODEL CHANGE= ARM|VISITNUM WABAQ TYPE AGE;
    REPEATED VISITNUM / TYPE= CS SUBJECT=SUBJID R RCORR;
  LSMEANS ARM*VISITNUM/pdiff CL;
RUN;
```

The least square (adjusted) mean for each treatment group, and the 95% confidence interval for the comparison (active vs. sham) will be presented at 1, 5, 20 weeks post treatment.

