9. HYPOTHESIS 1B

Hypothesis 1b: To address the hypothesis that the effect of A-tDCS will be greater in subacute stroke than reported in chronic stroke, the mean (95% CI) changes from baseline to 1 week, 5 weeks, and 20 weeks in PNT+Naming 80 after the end of treatment will be reported for the subacute patients enrolled in this project and the chronic patients from the CATES trial ([name], PI).

A figure of the adjusted mean of adjusted means (95% CI) at each time point for SLISSE Active, Sham using the repeated measures model described above will be shown alongside the adjusted means from CATES Active, Sham.

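### SAP 8.5 promises a sensitivity model adjusted for baseline, but its code has no baseline naming score, and Hypothesis 1b reuses that model

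*SAP*

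**What the plan says.** SAP 8.5 (Missing Data) plans a sensitivity analysis in the modified ITT sample that uses all follow-up data without imputation. The text calls it "a mixed effects model of the change from baseline in naming accuracy adjusted for baseline". It then says: "The model will include the baseline covariates used for the primary analysis as fixed effects". SAP 8.2 lists those covariates as aphasia type, AQ and age.

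The PROC MIXED code that follows in 8.5 reads "MODEL CHANGE= ARM|VISITNUM WABAQ TYPE AGE". Its CLASS statement holds only subject, arm, visit and type.

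Other places bear on the point:

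- The protocol (section 2, Primary Analyses, and section 7c, Statistical Analysis) uses the same wording for this model: "mixed effects model of the change from baseline in naming accuracy adjusted for baseline".
- SAP section 9 (Hypothesis 1b) will plot adjusted means "using the repeated measures model described above will be shown alongside the adjusted means from CATES Active, Sham". Its outcome is PNT+Naming 80, not PNT alone.
- SAP section 11, under Hypothesis 2b, names baseline naming accuracy as a covariate in its own right.
- SAP section 2 says that before database lock "this Statistical Analysis Plan (SAP) will be updated", and that the final SAP defines the pre-planned analyses "and will trump the protocol".

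**The concern.** An analyst who follows the text of 8.5 fits a model with the baseline naming score. An analyst who copies the code fits one without it. Both could claim to have followed the SAP, the two week-1 contrasts would differ, and the choice could be made after unblinding. The precedence rule in SAP section 2 does not settle it, because both versions stand inside the SAP.

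The term matters for what this model is meant to check. The response is change from baseline, so a participant with no post-treatment visit contributes nothing to the fit. Dropout that depends on baseline PNT is then covered by the missing-at-random assumption only if baseline PNT is among the covariates. SAP 8.4 tests sensitivity analyses at two-sided 0.05, so the result will be read as a formal check on the primary finding. Hypothesis 1b inherits the ambiguity and sets the resulting means beside those of another trial.

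**Working it through.** **1. Text against code (SAP 8.5)**

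| Term | Text | Code |
|---|---|---|
| Arm, visit | yes | yes, with their interaction |
| AQ, type, age | yes, in their own sentence | yes |
| Baseline naming score | yes, on its natural reading | no |

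Three things support that reading. The phrase directly follows change in naming accuracy. If it meant only AQ, type and age, the covariate sentence would be redundant. Hypothesis 2b treats baseline naming accuracy as a separate covariate. In addition, the protocol's sentence on this model names no other baseline covariate, so there the phrase cannot be shorthand for AQ, type and age.

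**2. The plan's own figure**

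Inputs from SAP 8.3: 20 per arm, difference 23, SD of change 22.2, two-sided alpha 0.05. The SE is 22.2 × √(2/20) = 7.02 and the noncentrality is 23/7.02 = 3.28. With 38 df the noncentral t gives 89.1%, which matches the stated 89%. That figure is for an unadjusted t-test and is unaffected by this point.

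**3. Size of the dropout bias in the coded model**

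The documents do not give the baseline to week-1 PNT correlation (r), the AQ to baseline PNT correlation (rho) or the baseline SD (s). Assumptions:

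- (r, rho) = (0.5, 0.6), (0.7, 0.8) or (0.9, 0.9).
- Baseline and week-1 SDs are equal, so s = 22.2/√(2(1 − r)).
- AQ acts only through baseline PNT.
- 20% are lost before week 1 and have no later visits.

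Let d be the difference between arms in mean baseline PNT among those observed, in SD units, after adjustment for AQ. The week-1 contrast without baseline is then biased by (1 − r) × s × d in absolute value. I obtained d by simulation (2,000,000 per arm, logistic dropout). In the first scenario the odds of dropout double per SD lower baseline PNT in one arm only. In the second the dependence runs in opposite directions in the two arms.

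| r, rho | s | d, one arm | Bias (items) | d, opposite | Bias (items) |
|---|---|---|---|---|---|
| 0.5, 0.6 | 22.2 | 0.082 | 0.5 × 22.2 × 0.082 = 0.9 | 0.170 | 1.9 |
| 0.7, 0.8 | 28.7 | 0.047 | 0.3 × 28.7 × 0.047 = 0.4 | 0.097 | 0.8 |
| 0.9, 0.9 | 49.6 | 0.026 | 0.1 × 49.6 × 0.026 = 0.1 | 0.052 | 0.3 |

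At 10% loss the bias is about half. With equal dependence in both arms, or with baseline in the model, it is zero apart from simulation noise. The sign depends on which arm loses the low-baseline participants. The check is a week-1 regression on arm and AQ, a simplification of the repeated-measures model.

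For scale, the residual SD is 19.2 to 21.7 over these settings with or without baseline, so the SE at 20 per arm is 19.2 × 0.316 = 6.1 to 21.7 × 0.316 = 6.9. The largest bias is about 0.3 of an SE (1.9/6.7 = 0.28).

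**4. The separate question of the primary regression**

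SAP 8.2 promises no baseline PNT, so nothing there is contradicted. To see whether adding it would help, I simulated trials with 20 per arm, a true difference of 23 and a regression on arm, AQ, age and two type terms. Power without and then with baseline PNT was about 89 to 93% at (0.5, 0.6), 88 to 89% at (0.7, 0.8) and 87 to 86% at (0.9, 0.9).

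**The case against.** The wording may be a leftover. The phrase also stands in the protocol, and the SAP then added a covariate sentence and code that may be all its authors meant. That is possible, so the fix must allow for it. It is the weaker reading for the reasons in step 1, and on either reading the section needs an edit.

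The bias scenario is also generous to the concern, and this objection stands:

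- The 20% comes from the protocol's 50 enrolled and 40 to 45 completing. That counts completion of the whole study, not loss before week 1.
- SAP section 4 aims for 50 participants with a week-1 PNT, and the modified ITT sample already leaves out those never treated.
- Bias needs dropout that depends on baseline differently by arm, and the documents give no reason to expect that in a double-blind trial.

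A reader might infer that the primary, secondary, subgroup and Hypothesis 2a models are wrong in the same way, since none includes the outcome's baseline and section 10 repeats the same MODEL line. The documents do not support that. The texts of 8.2, 10 and 11 for those models promise no such term. Under randomization its omission causes no bias on average. AQ includes a naming component and is balanced by the randomization, so it is a partial proxy for baseline PNT.

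**Conclusion.** The inconsistency is real and can be checked on the page: SAP 8.5 specifies one model in words and another in code, and Hypothesis 1b builds on it. The case rests on that contradiction in a pre-specified analysis, not on a large bias. The bias is roughly 0.1 to 2 items under the assumed correlations, 20% week-1 loss and arm-differential dependence. Without that differential it is zero.

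It would be too strong to conclude that the missing-data check is materially biased or that the primary result is in doubt. Adding baseline PNT to the primary regression is an optional improvement. Over the settings tried, its effect runs from a moderate power gain to none or a slight loss.

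**What to change.** At the SAP update planned before database lock, change the line in 8.5 to `MODEL CHANGE = ARM|VISITNUM BASE WABAQ TYPE AGE;`. Define BASE as the mean of the two pre-treatment PNT scores. SAP 8.1 already has the test "administered twice (and averaged to reduce variability) on two consecutive days immediately before treatment starts". This brings the code into line with the SAP text. A BASE*VISITNUM term, which lets the baseline slope differ by visit, is an optional extension that the text does not require.

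For Hypothesis 1b, state that BASE is the baseline of PNT+Naming 80. Check that the adjustment is comparable with that behind the CATES adjusted means before showing them together; these documents do not describe the CATES model.

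If baseline adjustment is not intended, delete the phrase from 8.5 and record the departure from the protocol.

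The cost is one line of code and one parameter (three with the optional interaction). The data are already collected. Hypothesis 1b also needs the comparability check.

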9. HYPOTHESIS 1B

Hypothesis 1b: To address the hypothesis that the effect of A-tDCS will be greater in subacute stroke than reported in chronic stroke, the mean (95% CI) changes from baseline to 1 week, 5 weeks, and 20 weeks in PNT+Naming 80 after the end of treatment will be reported for the subacute patients enrolled in this project and the chronic patients from the CATES trial ([name], PI).

A figure of the adjusted mean of adjusted means (95% CI) at each time point for SLISSE Active, Sham using the repeated measures model described above will be shown alongside the adjusted means from CATES Active, Sham.

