In this project, we intend to investigate whether tDCS combined with SALT improves naming individuals with aphasia in the acute and subacute post stroke period, more than tDCS alone in a randomized, double-blind, sham-controlled trial. We hypothesize that A-tDCS over a targeted region and computer-delivered SALT is associated with greater gains in accuracy in naming pictures, compared to sham combined with the same computer-delivered SALT in post stroke aphasia. We will compare the effect size in this study to the effect size obtained in the ongoing CATES trial (PI: [name], University of S. Carolina), which uses the identical computer-delivered SALT + tDCS vs sham in chronic stroke, to evaluate the optimal timing of tDCS after stroke. We will explore whether or not the use of selective serotonin reuptake inhibitors (SSRIs) modifies the effect of tDCS on SALT in acute and subacute stroke,

Date: March 2, 2021

Principal Investigator: [name], MA

Application Number: IRB00089018

and whether tDCS influences resting state connectivity in functional MRI (rsfcMRI) and/or functional Near-Infrared Spectroscopy (fNIRS).

We will also investigate the extent that the presence of genetic polymorphisms affect therapy outcomes. All participants will be asked to provide a saliva sample for the purpose of genotyping for BDNF (brain derived neurotrophic factor) and the FOXP2 gene (forkhead box p2). BDNF is a growth factor that has been shown to promote plasticity. Some individuals are carriers of the VAL66MET polymorphism, which leads to reduced BDNF secretion, and potentially decreased outcomes in aphasia therapy. Participants will be allowed to decline genetic testing. We will evaluate if there are any differences between participants who decline and those who agree to the testing.

The FOXP2 gene is the first gene that been implicated in speech-language impairment. Specifically, the FOXP2 polymorphism rs17137124. This gene has been implicated in neurogenesis and synaptogenesis, but little is known about its role in post-stroke recovery in humans. However, in a mouse model, FOXP2 expression has been related to the recovery of vocalization.

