Secondary Analyses: In secondary analyses, we will evaluate the effect of A-tDCS versus sham on change in lexical features of discourse, NIH Stroke Scale (NIHSS) (Lyden et al., 1999), modified Rankin Scale (mRS) (Banks et al., 2007; Rankin 1957), Stroke Impact Scale (Duncan et al., 1999) as well as Content Units (CU) and syllable/CU in the "Cookie Theft" picture description (Craig et al., 1993; Yorkston & Beukelman, 1980). Secondary analyses will also examine if any effects of A-tDCS vary across participants with different characteristics such as SSRI use, age, education, time of initiation of treatment, previous SALT, and lesion volume. To address this, a regression of change in naming accuracy, which includes main effects and interaction terms with treatment group for these characteristics will be used. This model will be adjusted for treatment and time as described above for the mixed effects model. Given the small sample size and since this is a secondary analysis, a significance level of 0.10 will be used to retain main effects or interaction terms with treatment in the final reported model. Finally, within the tDCS treatment group, we will compare mean change in naming untrained pictures for the fMRI localization versus the structural localization subgroups (n=10-13 per subgroup). If there is a trend for the fMRI localization subgroup to show greater gains than the structural localization subgroup, we will include this comparison in a Phase III trial.

Secondary Objectives

Date: March 2, 2021

Principal Investigator: [name], MA

Application Number: IRB00089018

Hypothesis 1b: The effect of A-tDCS will be greater in subacute stroke than reported in chronic stroke, the mean (95% CI) changes from baseline to 1 week, 5 weeks, and 20 weeks after the end of treatment will be reported for the subacute patients enrolled in this project and the chronic stroke patients enrolled in the Transcranial Direct Current Stimulation to Treat Aphasia: Phase II Trial (U01 DC011739; CATES Trial; PI: [name]) conducted at the University of South Carolina and the Medical University of South Carolina. The current trial is being conducted in collaboration with our colleagues at Medical University of South Carolina and University of South Carolina, including [name], who has designed and published previous studies using the computer-delivered SALT.

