Communication through language is central to the human experience. Disorders of language, such as post stroke aphasia, impede interaction and hamper interpersonal connections and reintegration into family life, work, and school (Wise, 2003). In the setting of post stroke aphasia, some degree of language recovery over time is common, mostly occurring within the first few months after stroke; however, severe and debilitating language deficits frequently persist, and decline in cognitive/language abilities and overall function can occur in those who do not receive SALT(Dhamoon et al, 2012; Iadecola, 2013).

SALT is the mainstay of treatment for individuals with aphasia (Brady et al., 2012; Kurland et al., 2012). Clinicians strive to provide evidence-based interventions to improve language abilities after stroke. Meta-analyses indicate that about 100 hours of SALT are needed to significantly improve functional communication (Bhogal et al., 2003). Therapy is beneficial for language recovery in stroke, especially in the first three months post stroke (Hillis, 2010; Lazar et al., 2010); however, gains in therapy are variable and progress may be slow, especially in the chronic stage for patients with large lesions in the left hemisphere (Bhogal et al., 2003; Brady et al, 2012). Transcranial direct current stimulation (tDCS) is one method that has been proposed to boost behavioral language treatment in post stroke aphasia (Baker et al., 2010; Fiori et al., 2011; [name] et al., 2011; Jung et al., 2011; Marangolo et al., 2013; You et al., 2011). Although the precise mechanism of tDCS is still emerging (Weiss & Bikson, 2014), the prospect of augmenting the effectiveness of behavioral therapy is attractive to clinicians, patients, and their families and caregivers.

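### SAP section 9 produces no estimate of the quantity in Hypothesis 1b: the difference between the subacute and chronic active-minus-sham effects

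*SAP*

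**What the plan says.** SAP section 9 states the hypothesis that "the effect of A-tDCS will be greater in subacute stroke than reported in chronic stroke". Two outputs are planned for it.

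- Text: means with 95% CI for "changes from baseline to 1 week, 5 weeks, and 20 weeks in PNT+Naming 80 after the end of treatment", which "will be reported for the subacute patients enrolled in this project and the chronic patients from the CATES trial". The sentence does not say that these are split by arm.
- Figure: adjusted means for this trial's Active and Sham arms, from the repeated measures model given earlier in the SAP, which "will be shown alongside the adjusted means from CATES Active, Sham".

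The protocol's wording under Hypothesis 1b (section 2, Objectives) has the same form: "the mean (95% CI) changes from baseline to 1 week, 5 weeks, and 20 weeks after the end of treatment will be reported" for the two sets of patients. The protocol's opening summary names the right target, "We will compare the effect size in this study to the effect size obtained in the ongoing CATES trial", with the aim of judging when after stroke tDCS works best, but it gives no estimator or interval. SAP section 2 makes the final SAP override the protocol.

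One component is already planned. Under SAP 8.5, "the 95% confidence interval for the comparison (active vs. sham) will be presented at 1, 5, 20 weeks post treatment". That covers this trial only, as a sensitivity analysis of the primary outcome.

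**The concern.** In a sham-controlled trial the effect of A-tDCS is active minus sham. Hypothesis 1b is therefore about a difference between two such differences, and section 9 stops at the ingredients. Four means with separate intervals, or two trial-level means, give neither an estimate nor a confidence interval for the hypothesised quantity.

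The direction of the risk is known. The protocol's Background says that "some degree of language recovery over time is common, mostly occurring within the first few months after stroke", and SAP 5.1 enrols within 90 days of stroke. Both subacute arms can improve for reasons unrelated to stimulation, so comparing active arms, or whole trials, leans towards the hypothesis. What is at stake is the statement about optimal timing that the protocol wants from this comparison.

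SAP section 11 already uses treatment interaction terms for effect modification within the trial, including by time since stroke. Section 9 does not carry that logic over to the comparison between trials.

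**Working it through.** **The plan's own figure.** The documents give no precision or power for Hypothesis 1b. The nearest figure is SAP 8.3: 20 per arm, difference 23, SD 22.2, two-sided alpha 0.05, power 89%. The standard error of active minus sham is 22.2 × √(2/20) = 7.02, so the noncentrality is 23/7.02 = 3.28. With 38 degrees of freedom the noncentral t gives 89.1%. The stated power reproduces.

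**What each comparison estimates.** Let r_S and r_C be the mean sham changes in the subacute and chronic trials, and e_S and e_C the active-minus-sham effects.

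- Active arm against active arm: (r_S − r_C) + (e_S − e_C).
- Whole trial against whole trial, with 1:1 allocation in both (stated for this trial, assumed for CATES): (r_S − r_C) + (e_S − e_C)/2.
- Difference of active-minus-sham effects: e_S − e_C.

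Only the third is the quantity in Hypothesis 1b. The first two carry r_S − r_C, which is positive if subacute sham patients recover more than chronic ones.

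**Precision of the right contrast.** With n per arm here and m per arm in CATES, SE = SD × √(2/n + 2/m). Inputs:

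- SD 22.2 from SAP 8.3, assumed to hold in all four arms and for PNT+Naming 80;
- n = 20 from SAP 8.3;
- m = 20 to 40, an assumption, since the documents do not give the size of CATES.

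| m per CATES arm | SE | 95% CI half-width (1.96 × SE) | Difference in effects detectable with 80% power (2.80 × SE) |
|---|---|---|---|
| 20 | 22.2 × √0.20 = 9.93 | 19.5 | 27.8 |
| 40 | 22.2 × √0.15 = 8.60 | 16.9 | 24.1 |

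SAP section 4 aims for 50 patients with a week 1 PNT. With n = 25 the SE is 22.2 × √0.18 = 9.42 to 22.2 × √0.13 = 8.00, and the half-width 18.5 to 15.7.

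So the contrast would reliably detect only a difference in effects about as large as the whole assumed effect of 23. These are unadjusted, normal-approximation figures. Covariate adjustment may narrow them.

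**The case against.** The case for leaving section 9 alone has real content.

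- The figure shows both sham arms. Spontaneous recovery would lift the subacute sham means beside the active ones, and a reader could subtract by eye. This stands as a partial safeguard, but it yields no estimate or interval for the difference in effects.
- This trial's half of the contrast is nearly in hand. The SAP 8.5 code requests pairwise least-squares mean differences with confidence limits, and section 9 uses that model. This also stands, though 8.5 applies it to the primary outcome, not PNT+Naming 80, and nothing equivalent is stated for CATES.
- The protocol's opening summary promises a comparison of effect sizes, and section 9 does not contradict it. The intention is therefore right and the calculation is missing.
- Hypothesis 1b is secondary. The Phase III decision in protocol section 7c rests on the primary null hypothesis.

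A reader might go further and infer that the plan has a high false-positive rate for 1b. Suppose the tDCS effect is identical in both trials, the whole assumed sham change of 10 is subacute recovery, and chronic sham change is zero. An active-versus-active test would then have z = 10/(22.2 × √(1/20 + 1/m)) = 1.42 to 1.64 for m = 20 to 40, and would be significant in favour of subacute stroke 30% to 38% of the time. The documents do not support that as a property of the plan:

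- No such test, p-value or decision rule is planned.
- Zero chronic sham change is extreme, because sham patients in both trials receive the same computer-delivered therapy and Naming 80 consists of trained items. With an excess of 5 items the rate is about 11% to 13% (m = 20 to 50).
- The 10 and 22.2 are planning values for a different outcome, and the CATES sizes are assumed.

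**Conclusion.** The point holds as a mismatch between hypothesis and output. SAP section 9 states a hypothesis about a difference in effects, and nothing in either document estimates that difference or its uncertainty. Any comparison of arm-level or trial-level means across the two trials is biased towards the hypothesis to the extent that subacute sham patients improve more than chronic ones, which the protocol's account of early recovery leads one to expect. The documents do not allow the size of that bias to be fixed.

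The inference that recovery will simply pass for a larger tDCS effect goes too far, because both sham arms are displayed. The primary analysis and the Phase III decision are untouched.

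The half-width of about 17 to 19.5 items rests on an SD of 22.2 in all arms, 20 per arm here and 20 to 40 per arm in CATES. It also reads the planning values as items, although SAP 8.3 gives no unit for change in accuracy. The mismatch and the direction of the bias do not depend on these numbers.

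**What to change.** In the SAP update that section 2 foresees before database lock, amend section 9 as follows.

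1. At weeks 1, 5 and 20, report active minus sham with its 95% CI for PNT+Naming 80 in each trial, using the same adjustment model in both where possible (aphasia type, AQ, age).
2. Report the subacute-minus-chronic difference of these two effects at each week with its 95% CI, from the two estimates and standard errors: SE = √(SE_subacute² + SE_chronic²).
3. Label the result exploratory and non-randomised between trials, and describe the arm-level means and the figure as descriptive only. State that the text means are given by arm.

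The cost is small. For this trial the planned model, run on PNT+Naming 80, already prints the contrast. From CATES only the corresponding estimate and standard error are needed. The downside is a wide interval that will rarely settle the question of timing, but it makes visible an uncertainty that four separate intervals do not show.
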